## Questions that each state of the experiment could address

### ***Resting state***

1. Brain signals (MEG/EEG/LFPs) recorded during rest sections of the task: the baseline of targets' local field potentials and patients' pain scale.
2. Signals recorded during easy task sections: the response of the targets to the endogenous pain modulation (compared with baseline signals).
3. Signals recorded during difficult task sections: the response of the targets to the endogenous pain modulation (compared with baseline signals)
4. The change of targets' brain signals with different degrees of pain modulation (easy versus difficult task)

### ***Therapeutic Stimulation state***

1. Brain signals recorded during rest sections of the task: Stimulation effect on the targets
2. Brain signals recorded during easy and difficult sections of the mental task: compared with the data gathered in resting state, we can see if stimulation can enhance the endogenous pain modulation or have no effect on it.

### ***Medication state***

1. Brain signals recorded during rest sections of the mental task: Drug effects on the targets
2. Brain signals recorded during easy and difficult sections of the mental task: compared with the data gathered from resting state, we can see if medications can enhance endogenous pain modulation or have no effect on it.

### ***Pain stimulation state***

1. Brain signals recorded during rest sections of the mental task: pain signatures of the targets induced by painful stimulus
2. Brain signals recorded during easy and difficult sections of the mental task: we can investigate how endogenous pain modulation affects the pain signatures induced by painful stimulus

## **Informed Consent**

Informed consent to this study will be obtained prior to the participants' inclusion in the study. In addition, verbal consent will also be acquired at the point of each research intervention. The patients will be supplied with Patient Information Sheets in advance of the surgery while participants will be provided with the Healthy Volunteer Information Sheet at least 2 weeks prior to involvement in any imaging or testing. Consent will be taken by the pain nurse or someone else independent of the direct care team.

## **Definition of End of Study**

The end of study is the date of the last research experiment of the last participant.

## INTERVENTIONS

Pre-operatively and Post-operatively we will perform microneurography, QST, tilt table tests, ECG, ambulatory blood pressure, and GSR.

During the distraction and MEG/LFP experiments we will measure patients' ECG, blood pressure and respiratory rate. We will also record their LFPs, MEG, EEG and visual analog scale of pain. In order to know the neural signature for pain, we will use painful stimulation to induce patients' pain perception. This stimulation will take the form of Contact Heat-Evoked Potential Stimulation, electrical stimulation, or mechanical stimulation, with selective stimulation of A-Delta & C-fibers.

## SAFETY

There is no risk that participants are exposed to other than they may experience more pain or a different type of pain to their usual pain. Patients will be given the ability to stop the experiment at any time should they feel uncomfortable.

### Definition of Serious Adverse Events

A serious adverse event is any untoward medical occurrence that:

Results in death,

Is life-threatening,

Requires inpatient hospitalisation or prolongation of existing hospitalisation,

Results in persistent or significant disability / incapacity, or

Is a congenital anomaly / birth defect.

Other important medical events.\*

NOTE: The term "life-threatening" in the definition of "serious" refers to an event in which the participant was at risk of death at the time of the event; it does not refer to an event which hypothetically might have caused death if it were more severe.

\*Other events that may not result in death, are not life threatening, or do not require hospitalisation, may be considered a serious adverse event when, based upon appropriate medical judgement, the event may jeopardise the participant and may require medical or surgical intervention to prevent one of the outcomes listed above.

### Reporting Procedures for Serious Adverse Events

A serious adverse event (SAE) occurring to a participant should be reported to the REC that gave a favourable opinion of the study where in the opinion of the Chief Investigator the event was 'related' (resulted from administration of any of the research procedures) and 'unexpected' (the type of event is not listed in the protocol as an expected occurrence). Reports of related and unexpected SAEs should be submitted within 15 days of the Chief Investigator becoming aware of the event, using the NRES report of serious adverse event form (see IRAS/NRES website).

## STATISTICS AND ANALYSIS

### Number of Participants

The expected number of participants involved in this study is approximately 50. This is based on the annual number of neuromodulation operations for pain relief at the John Radcliffe Hospital.

### Analysis of Outcome Measures

Outcome measures of both intervention group and control group (QST, EEG/MEG) will be analysed using statistical analysis software and MATLAB. All participant data will be utilized in analysis unless they have withdrawn consent.

### Analysis of Endpoints

The endpoint analysis will be performed using statistical analysis software and mathematical computational modeling licensed by the University of Oxford. The analysis involves complex signals analysis techniques where significant difference in power at certain frequencies can be determined using custom-made software (based on MATLAB®).

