## SYNOPSIS

Study Title	The cerebral signature for pain perception and its modulation
Study Design	Prospective study
Intervention Group	All chronic neuropathic pain patients treated with deep brain Stimulation, Spinal Cord Stimulation including targeted stimulation of the Dorsal Root Ganglion, and noninvasive neurostimulation.
Number in Intervention Group	Approximately 50 patients minimum
Control Group	Healthy volunteers with no history of chronic pain, no acute pain, no previous neurosurgery and , no neurological/psychiatric comorbidities.
Number in Control Group	Approximately 50 minimum
Planned Study Period	September 2013 to December 2019
Primary Objective	To determine whether there is cerebral pain signature
Secondary Objectives	To understand how the cerebral pain matrix, including brainstem, anterior cingulate cortex, thalamus and cerebral cortex interact with one another and with the spinal cord and dorsal root ganglia for pain perception and its modulation. Also, to determine whether stimulation has an effect on the autonomic nervous system.
Primary Endpoint	Differences of LFPs of various cerebral nuclei induced by endogenous pain modulation and DBS in chronic pain compared to healthy controls

Secondary Endpoints	Differences of LFPs of various cerebral nuclei induced by Analgesics, Difference in Muscle Sympathetic Nerve Activity (MSNA), Magnetoencephalographic (MEG) or Electroencephalographic (EEG) signals on and off stimulation and other autonomic parameters
Intervention (s)	Quantitative Sensory Testing, and patients' everyday analgesics, Micro-neurography, EMG, and LFP, EEG or MEG recording of brain or DRG, Non-invasive brain stimulation (TMS/tDCS) in chronic pain compared to healthy controls

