## OBJECTIVES

### Primary Objective

To determine whether there is a cerebral pain signature

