#### Chronic pain patients:

##### Inclusion Criteria

Patients who are willing and able to give consent to the study.

Male or Female, aged 18 years or above.

Treatment includes DBS of ACC, PAG or sensory thalamus (VPL or VPM), SCS or DRG stimulation, or peripheral analgesic stimulation.

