### **Distraction mental task**

The task includes 15 sections, including 5 rest, 5 easy and 5 difficult ones. Each section lasts around one minute. The sequence of these sections will be randomised.

In the rest section patients will just need to concentrate on their pain, and after the section patients will choose a score on the visual analogue scale on the screen, indicating how their pain is during the section.

In the easy task section patients will need to remember the colour of the T-shape figure shown on the screen before starting the easy section. When the section begins, the screen will show many T-shape figures, one by one, with various colours. Whenever seeing the correct colour, as shown before the section, patients need to push a button of the computer's keyboard. After the section patients will choose a score on the visual analogue scale, indicating how their pain is during the task section.

In the difficult task section patients will need to remember the colour and the orientation of the T-shape figure shown on the screen before starting of the section. When the section begins, the screen will show many T-shape figures, one by one, with various colours and orientations. Whenever seeing the figure with the correct colour and orientation patients need to push a button of the computer's keyboard. After the section patients will choose a score on the visual analogue scale, indicating how their pain is during the task section.

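### The primary LFP endpoint names a healthy-control comparison that cannot be made, and its significance analysis fixes no target, contrast, alpha, frequency range, unit of analysis or error control

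*Combined protocol and SAP*

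**What the plan says.** The Primary Objective is a yes/no question: "To determine whether there is a cerebral pain signature". The Synopsis gives the primary endpoint as "Differences of LFPs of various cerebral nuclei induced by endogenous pain modulation and DBS in chronic pain compared to healthy controls".

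The statistics chapter has three short sections. Number of Participants gives about 50, taken from annual caseload. Analysis of Outcome Measures names software, lists QST and EEG/MEG as the measures for both groups, and says all data are used unless consent is withdrawn. Analysis of Endpoints says that a "significant difference in power at certain frequencies can be determined using custom-made software".

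Candidate comparisons appear elsewhere. The patient inclusion criteria list ACC, PAG and sensory thalamus as DBS targets. The Resting state section lists easy and difficult task sections against baseline, and easy against difficult. The Therapeutic Stimulation state section adds the stimulation effect at rest and a comparison from which "we can see if stimulation can enhance the endogenous pain modulation or have no effect on it". None of these is marked as primary.

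**The concern.** There are two separate defects.

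First, the primary endpoint as worded needs LFPs from healthy controls, and the protocol's own eligibility and procedure sections rule these out.

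Second, the primary analysis rests on statistical significance while target, contrast and frequency stay open. A reader of the results could not tell how many comparisons lay behind a significant frequency, or whether patients, hemispheres, electrodes or task sections were counted as independent. If the comparisons are unadjusted, the error rate on the primary question exceeds the nominal level.

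The choice of contrast also affects what a result means. For rest sections the plan says "In the rest section patients will just need to concentrate on their pain". In task sections patients also search a screen and press a key, so a rest-versus-task difference need not be about pain.

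**Working it through.** **1. The plan's own figure.** About 50 participants (Number of Participants), or about 50 minimum in each group (Synopsis). No alpha, power, effect size or SD is given, so the figure cannot be reproduced. Cerebral LFPs need cerebral electrodes, and the number of DBS patients is not stated, so the n for this endpoint may be well below 50.

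**2. Control data, section by section.**
- Study Design and Procedure (Intervention Group): LFPs are recorded from the implanted electrodes, between the two operations.
- Controls, Exclusion Criteria: any past neurosurgery excludes.
- Control Group procedure, endpoints and outcome measures, and Analysis of Outcome Measures: MEG/EEG for controls, no LFP.

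The number of control LFP recordings is therefore zero.

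**3. What is left open.** Effects: 2 (endogenous modulation, DBS). Targets: 3, or 4 if VPL and VPM are counted separately. Contrasts for the two effects: easy–rest, difficult–rest, easy–difficult, stimulation at rest, and the change in endogenous modulation under stimulation. That makes 5, or 6 if the last is split by easy and difficult.

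**4. Chance of at least one false positive if unadjusted.** Assumed: two-sided 0.05 and no true effect. For m independent tests the formula is 1 − 0.95^m. The simulations allow for correlation: contrasts share the cells of a 2-state by 3-task layout within each patient (4,000 runs), and neighbouring bins are correlated.

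| Family | m | 1 − 0.95^m | Simulated |
|---|---|---|---|
| Two effects, one target, one band | 2 | 0.098 | 0.088–0.095 (n = 6 to 25) |
| Five contrasts, one target, one band | 5 | 0.226 | 0.181–0.193 (n = 6 to 25) |
| Five contrasts, three targets, one band | 15 | 0.537 | 0.26–0.46 (n = 6 to 25; correlation between targets 0.9 to 0) |
| One contrast, 40 bins | 40 | 0.871 | 0.36–0.84 (n = 6 to 20; adjacent-bin correlation 0.95 to 0.5) |

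Counting six contrasts in the second row gives about 19 to 23%.

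**5. Unit of analysis.** Each condition has 5 sections. If section values are tested as independent but correlate within a patient by ICC, the variance is inflated by 1 + (5 − 1) × ICC. The true level is then 2 × [1 − Φ(1.96/√inflation)]. For assumed ICC 0.1, 0.3, 0.5 and 0.8 the inflation is 1.4, 2.2, 3.0 and 4.2, and a nominal 5% becomes about 10%, 19%, 26% and 34%.

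**6. A controlled alternative.** Take one value per patient per bin, flip the sign of each patient's whole spectrum at random, and compare the largest statistic across the 40 bins with its permutation distribution. The simulated error is 0.029–0.062 (n = 6 to 20, 2,000 runs).

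**7. Its cost.** For a 0.5 SD within-patient effect in 5 of 40 bins, power at the 5% level is about 5% at n = 6 and 30 to 38% at n = 20. The smallest possible two-sided sign-flip p is 2/2^n: 0.0625 at n = 5, 0.031 at n = 6 and 0.016 at n = 7. A first step at 0.025 is thus out of reach below seven patients. This is a floor on p, not a sample size.

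**8. Does any contrast isolate pain?** Assume n = 20 and a 0.5 SD task shift in 5 bins that has nothing to do with pain. Difficult–rest rejects 78% of the time. Easy–difficult rejects 4.7% with no load effect, 16.5% with a 0.25 SD load effect and 77% with a 0.5 SD load effect. Neither contrast separates pain from task demands.

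**The case against.** The strongest reply is that the plan does not let just any significant frequency count as a signature. Rationales behind this protocol looks for correlation with the VAS and for change under endogenous or exogenous modulation. Non-invasive Brain Stimulation adds targeted stimulation to separate pain signalling from an epiphenomenon. This stands: a reader might infer from Analysis of Endpoints that one nominal finding would answer the primary question, and the documents do not support that. But neither section says what result suffices, at what level or in which contrast, so the gap in the analysis remains.

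A reader might also infer that no correction will be applied. The plan neither states nor excludes one, so the error rates are conditional.

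On the controls, it is fair to say that the fault lies mainly in the Synopsis wording. The section on endpoints and outcome measures already keeps LFPs to the intervention group and gives controls MEG/EEG, and Analysis of Outcome Measures agrees. It does not follow that the study lacks a usable control comparison.

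Finally, one could argue that easy versus difficult must be the primary contrast because both involve search and key presses. The documents do not settle this. The Resting state section defines the response to endogenous modulation against baseline, and if both tasks relieve pain equally, easy versus difficult is null although modulation is real. Task load still differs as well.

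**Conclusion.** The concern holds in two parts. The LFP comparison with healthy controls in the Synopsis cannot be made; this follows from the documents alone and needs no assumption. The primary analysis is also unspecified in target, contrast, alpha, frequency range, unit of analysis and error control.

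The size of the second part is illustrative, because the documents give no alpha, bins, patients per target or correlations. The direction does not depend on those choices: with only two effects, unadjusted testing at 5% already gives about 9 to 10%, and an unadjusted scan over frequencies gives far more. Within-patient LFP contrasts and patient-versus-control MEG/EEG comparisons remain feasible, so the study can be repaired by specification.

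**What to change.** 1. In the Synopsis, restate the primary endpoint as within-patient LFP change in the intervention group, and make the healthy-control comparison MEG/EEG only, in line with the section on endpoints and outcome measures.
2. In Analysis of Endpoints, before LFP results are analysed, fix a two-sided 5% alpha, one primary target chosen without reference to LFP results, a frequency range with bin width, and one endogenous-modulation contrast from the Resting state list. The sponsor chooses task versus rest or easy versus difficult, and states that either may reflect task demands and not pain alone. The study period starts in 2013 and the listed amendment dates from 2018, so any LFP data already examined should be declared.
3. Use one value per patient per frequency and a patient-level sign-flip max-statistic or cluster permutation test.
4. Treat the endogenous and DBS effects as co-named, with Holm or a split alpha across them. A fixed sequence would block any DBS claim whenever the first contrast failed, and the endpoint gives the two no order. State 1 requires at least 24 hours without everyday pain medication; the State 2 text does not give medication status. The two passages must be reconciled before their difference is read as a stimulation effect.
5. Report other targets, states and modalities as exploratory or Holm-corrected, and keep the VAS correlation as part of the evidence for a signature.

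The cost is SAP wording and a standard routine in the MATLAB environment already named, with no new data. Fewer nominally significant frequencies can be claimed. Power falls below the step 7 figures wherever Holm or an equal split requires 0.025, and at n = 6 it is then zero. A narrower frequency range or a single band reduces this loss.

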## ETHICAL AND REGULATORY CONSIDERATIONS

### Declaration of Helsinki

The Investigator will ensure that this study is conducted in accordance with the principles of the Declaration of Helsinki

### Guidelines for Good Clinical Practice

The Investigator will ensure that this study is conducted in accordance with relevant regulations and with Good Clinical Practice.

### Approvals

The protocol, informed consent form, participant information sheet and any proposed advertising material will be submitted to an appropriate Research Ethics Committee (REC), and HRA for written approval.

The Investigator will submit and, where necessary, obtain approval from the above parties for all substantial amendments to the original approved documents.

### Reporting

The CI shall submit once a year throughout the study, or on request, an Annual Progress report to the REC Committee, HRA (where required) host organisation and Sponsor. In addition, an End of Study notification and final report will be submitted to the same parties

## **Participant Confidentiality**

The study staff will ensure that the participants' anonymity is maintained. The participants will be identified only by initials and a participants ID number on the CRF and any electronic database. All documents will be stored securely and only accessible by study staff and authorised personnel. The study will comply with the Data Protection Act which requires data to be anonymised when it is practical to do so.

## **Expenses and Benefits**

Reasonable travel expenses for any visits additional to normal care will be reimbursed on production of receipts, or a mileage allowance provided as appropriate.

## **Other Ethical Considerations**

This study does not require any involvement of vulnerable participants, participants who are unable to consent for themselves or indemnity provision.

In the unlikely event of seeing any structural abnormalities on an MRI scan, the scan will be checked by a clinical specialist. If the specialist feels that the abnormality was medically important, they will discuss the implications with the participant and arrange for further investigations as necessary. Participants will not be informed unless the doctor considers the finding has clear implications for their current or future health. It is important to note that scans are not carried out for diagnostic purposes, and therefore the scans are not a substitute for a clinical appointment. Rather, the scans are intended for research purposes only.

## **DATA HANDLING AND RECORD KEEPING**

The participants will be identified by a study specific participant number. The name and any other identifying detail will NOT be included in any study data electronic file.

## **Publication Policy**

The investigators will be involved in reviewing drafts of the manuscripts, abstracts, press releases and any other publications arising from the study. Authorship will be determined in accordance with the ICMJE guidelines and other contributors will be acknowledged.

## **FINANCE AND INSURANCE**

### **Funding**

The late [name] [name] Legacy Grant as attached.

## Insurance

The University has a specialist insurance policy in place which would operate in the event of any participant suffering harm as a result of their involvement in the research (Newline Underwriting Management Ltd, at Lloyd's of London). NHS indemnity operates in respect of the clinical treatment that is provided.

**APPENDIX B: Flowchart of patient events**

## Flowchart of Healthy volunteer events

**APPENDIX C: AMENDMENT HISTORY**

Amend- ment No.	Protocol Version No.	Date issued	Author(s) of changes	Details of Changes made
7	7	28/01/2018	[name], [name]	This amendment makes provision for the recruitment of a healthy control group, acquisition of a pre-operative MRI in chronic pain participants, as well as the use of non-invasive brain stimulation (TMS/tDCS).
